7 STUDY PROCEDURES AND SCHEDULE

7.1 STUDY PROCEDURES/EVALUATIONS

7.1.1 STUDY SPECIFIC PROCEDURES

The table below in section 7.3.4 highlights study specific procedures. Only patients who sign written informed consent will undergo study specific procedures.

7.1.2 STANDARD OF CARE STUDY PROCEDURES

Except for the ED phase of management, there will be no other change to standard of care procedures for either treatment arm. Patients will continue to be followed during hospitalization, with at least one LUS performed within 48 hours of randomization. (Later than this window, but no more than 96 hours, is at the discretion of the site PI)

7.2 LABORATORY PROCEDURES/EVALUATIONS

7.2.1 CLINICAL LABORATORY EVALUATIONS

Lab testing will be analyzed by the clinical lab at each respective institution for baseline chemistry and hemoglobin/hematocrit values. This reflects our pragmatic approach. If routine labs are performed clinically within 6 hours of the follow up time-point, these results will be used for study purposes (Table 2). If routine lab work is not drawn, the closest clinical lab draw will be recorded in the eCRF unless already recorded (i.e. the baseline value). NO labs will be drawn for study purposes.

7.3 STUDY SCHEDULE

7.3.1 SCREENING

A signed and dated informed consent form will be obtained before any study-specific screening procedures are performed. Results of evaluations obtained as part of routine medical care, which are performed prior to obtaining informed consent, may be used in place of the protocol-specified evaluations. Patients will acknowledge and agree to the use of this information for the study by giving informed consent.

At the Baseline Visit, patients will be assigned by the Internet Web-based Randomization System (IWRS) a unique permanent identification number (referred to as the patient identification number) such that all randomized patients from each center are given consecutive identification numbers by the IWRS in successive order of inclusion. We will utilize the REDCap randomization module.

Prospective study patients will have presented to the hospital for urgent therapy for AHF. Potential patients will be identified either en route to or upon arriving at the ED/hospital. Routine assessments associated with usual patient care may be used for the purposes of screening and may be completed in any order. Study specific procedures must be completed only after Informed Consent is obtained.

Patients may be enrolled at anytime during their ED stay, but preferably within 3 hours of first placement in a room in the emergency department. Time spent in the waiting room will not count towards these 3 hours.

The following procedures will be performed prior to or during Screening:

- Obtain written informed consent (must be performed as the first study-specific procedure)
- Review of prior medical history
- Review of prior and concomitant medications
- Physical examination (including height and weight when reasonably possible)
- Vital signs measurements (includes systolic and diastolic blood pressures, heart rate, body temperature, oxygen saturation reading and respiratory rate)
- 12-Lead Electrocardiogram
- Chest X-Ray (this is not a requirement however, for inclusion)
- Blood collection for local laboratory tests, including BNP or NT-proBNP, and pregnancy test if applicable.
- Inquiry about Adverse events

7.3.2 ENROLLMENT/BASELINE

Patients who continue to fulfill all of the eligibility criteria will be randomized. In regards to the SBP; a single recording below 120mmHg does NOT disqualify the patient as long as the SBP returns > 120mmHg. Randomization will occur via central IWRS system.

7.3.3 FOLLOW-UP & FINAL STUDY VISIT

Patients will be followed for a maximum of 30 days post-discharge. There will be NO further in-person visits once discharged. Patients will be called however at 30 days post-discharge ((+)) 30 business days or at the discretion of the local site PI to assess vital status and re-hospitalizations or ED visits.

7.3.4 SCHEDULE OF EVENTS TABLE

Schedule of Events	Screening	Day 1 T00	Day 1 T02-04	Day 1 T06	Day 2-6 T24-D6	30 day follow up
Informed consent (I/E)	X					
Medical History	X					
Medication history	X					
Clinical Assessment#		X	X	X	X	
Body Weight, height, Vital Signs	ED SOC	VS only	VS only	VS only	BW/VS only	
5-point and 7-point Likert scale		X		X	X	
Labs: Electrolytes, hematology, NP, eGFR, Troponin	ED SOC					
12-lead ECG	ED SOC					
CXR	ED SOC					
LUS B-lines 8 zone	X (LUS T00)		X	X	X ^{^^}	
Nitrate vs. Diuretic intense management		X	X	X		
Lab draw: eGFR, Hgb/Hct [^]		X				
eCRF/data collection/verification		X				X
Assessment of AE/SAE's						X
Phone follow-up Vital Status						X

Subject payment		X				X
-----------------	--	---	--	--	--	---

SOC = standard of care, ED = Emergency Department, I/E = inclusion, exclusion, CV = cardiovascular, LUS = lung ultrasound, BW = body weight, NP = natriuretic peptide ^if collected as part of standard of care, will use that result. The last collected result will be used if not drawn on or close to discharge ^^ LUS to be performed up to 48 hours after hospitalization. If an obs unit patient, prior to discharge.

Further detail regarding timing of assessments: [NOTE: given clinical circumstances (i.e. left the ER for a test, discussion with consultant, etc) – the SITE PI has final discretion to continue to image a patient before or after the allotted window. This time MUST be recorded in the eCRF]

- T00: initial LUS scan (in ED for screening and eligibility)
- T02: 2-4 hours after initial treatment (in ED) (+/- 30 minutes)
- T06: 2-4 hours after T02 or pre-ED discharge, whichever comes first (+/- 60 minutes)
- T48: up to 48 hours after initial scan (Day 3) (+/- 12 hours)

** For vital signs during hospitalization. The nearest vital signs to the LUS exam will be captured.

7.5 CONCOMITANT MEDICATIONS

All medications administered within 14 days prior to and during screening will be recorded in the case report form. Medications that are not specifically prohibited are permitted at the Investigator's discretion.

7.6 PROHIBITED MEDICATIONS, TREATMENTS, AND PROCEDURES

No medications, treatments, or procedures are prohibited unless specifically mentioned in the eligibility criteria. Patient safety and well-being are paramount: Any treatment deemed necessary may be utilized at the investigators discretion should there be any concern for the patients health.

8 ASSESSMENT OF SAFETY

8.1 SPECIFICATION OF SAFETY PARAMETERS

Mortality, re-hospitalization, and ED visits through 30 days will be assessed for safety as well as efficacy

Hypotension, defined as a SBP < 100mmHg or decrease > 60mmHg from baseline, will be assessed as a safety endpoint. SBP Decrease Safety Margin: Patients whose SBP decreases to < 100mmHg at any time (measurement must be repeated twice, 15 minutes apart, unless symptomatic) or who develop evidence of clinical hypotension (i.e. weakness, dizziness, faint, chest discomfort) despite a SBP > 100mmHg will be immediately assessed and treated as needed, and all further strategy of care interventions will be halted. Patient safety and care is paramount and takes precedence over all other considerations. The clinical team may halt the study at any time. If there are any questions, the PI or designee will make the final decision.

8.1.1 DEFINITION OF ADVERSE EVENTS (AE)

The Investigator and study staff are responsible for detecting and recording AEs and SAEs during scheduled safety evaluations and whenever such information is brought to their attention. This section of the protocol provides definitions and detailed procedures to be followed. During the follow up visit, the Investigator will question the patient about adverse events using an open question, taking care not to influence the patient's answers, e.g. "Have you had any unusual symptoms or medical problems since the last visit? If yes, please describe."

An AE is any unfavorable and unintended sign, symptom, or disease temporally associated with the use of an investigational (medicinal) product or other protocol-imposed intervention, regardless of attribution.

This includes the following:

- AEs not previously observed in the subject that emerge during the protocol-specified AE reporting period.
- Complications that occur as a result of protocol-mandated interventions
- Preexisting medical conditions (other than the condition being studied) judged by the investigator to have worsened in severity or frequency or changed in character during the protocol-specified AE reporting period.
- Abnormal laboratory values that fall into an abnormal range based upon the hospital's laboratory standards, the abnormality was not preexisting prior to enrollment, and the abnormality leads to a new treatment within the AE time frame

The AE and SAE reporting period extends to day 5 of hospitalization or discharge, whichever comes first, unless otherwise specified.

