8.4 REPORTING PROCEDURES

8.4.1 ADVERSE EVENT REPORTING

The study period during which AEs must be reported begins after informed consent is obtained and initiation of study treatment and for 5 days after ending study treatment. Patients will be followed for 30 days for ED visits, re-hospitalization, and mortality. Subject's hospital discharge summaries will be examined at hospital discharge and all non-exempt AEs will be investigated by examining necessary medical records.

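### After treatment starts, the schedule places adverse-event assessment only at the 30-day follow-up, so mild, short-lived symptoms depend on unsolicited report or late recall

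*Combined protocol and SAP*

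**What the plan says.** **When the patient is asked.** Section 8.1.1 states: "During the follow up visit, the Investigator will question the patient about adverse events using an open question". Its sample wording asks about problems since the previous visit. The same section tells staff to detect and record events at safety evaluations that it calls scheduled, and whenever they are told of one. It does not say which evaluations these are.

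**What the follow-up contact is.** Section 7.3.3 says: "There will be NO further in-person visits once discharged". It continues: "Patients will be called however at 30 days post-discharge", with an allowance of 30 business days or the site PI's discretion. The stated purpose is "to assess vital status and re-hospitalizations or ED visits"; adverse events are not listed.

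**The schedule.** In section 7.3.4 the row "Assessment of AE/SAE's" has one mark, in the 30-day column. T00, T02-04, T06 and Day 2-6 are blank on that row, although clinical assessment and vital signs are marked at all four. Section 7.3.1 lists an adverse-event inquiry at screening.

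**The reporting period.** Section 8.1.1: "The AE and SAE reporting period extends to day 5 of hospitalization or discharge, whichever comes first, unless otherwise specified". Section 8.4.1 gives a different period, which "begins after informed consent is obtained and initiation of study treatment and for 5 days after ending study treatment".

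**Other capture.** Section 8.1 makes hypotension a safety endpoint and calls for immediate assessment of low pressure or symptoms of hypotension. Section 8.4.1 has discharge summaries examined, and other medical records where needed.

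**The concern.** Objective 1 asks whether the nitrate strategy reduces congestion safely. Treatment lasts six hours, and section 2.3.1 expects several nitrate effects that are early and felt by the patient, such as headache soon after use, flushing and nausea. The diuretic risks named there (kidney injury, volume and electrolyte depletion) show up more in laboratory values, which are taken from routine care. A plan that does not schedule a question to the patient during or soon after treatment is therefore weakest for the symptoms named mainly for one arm.

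The trial is unblinded (section 10.6.1), so what patients volunteer and what staff write down may differ by arm. Section 10.4.5 reports safety events by arm and tests categorical data between arms, and the pilot is meant to inform a definitive trial. Incomplete or uneven symptom counts would carry into both uses. The documents do not allow the direction of any bias to be stated.

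**Working it through.** The plan states no figure on this point, so there is none to reproduce. The check is a reading of the schedule followed by date arithmetic.

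**1. Every listed adverse-event question to the patient**
- Screening (7.3.1): before treatment.
- T00, T02-04, T06, Day 2-6 (7.3.4): no mark on the adverse-event row.
- 30-day column (7.3.4): one mark.
- The follow-up visit (8.1.1): no time given. Section 7.3.3 defines only one follow-up contact, the call, and the schedule's mark sits in the same column. I infer that they are the same contact.

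**2. Gap between the close of the reporting period and the call**

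Let day 1 be the day of treatment, L the day of discharge, and E the day treatment ends.
- Call: day L + 30. With the full allowance, 30 business days = 6 weeks = 42 calendar days, so day L + 72.
- Section 8.1.1 period closes on day min(5, L). Gap = L + 30 − min(5, L).
- Section 8.4.1 period closes on day E + 5. Gap = L + 30 − (E + 5).

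The documents give no length of stay, so L is assumed to run from 1 to 10. The table takes E = 1, since treatment lasts six hours (6.1.2).

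| L | Gap, 8.1.1 period | Gap, 8.4.1 period | Same two gaps with full allowance |
|---|---|---|---|
| 1 | 30 days | 25 days | 72 and 67 |
| 5 | 30 days | 29 days | 72 and 71 |
| 10 | 35 days | 34 days | 77 and 76 |

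The lower bounds do not depend on the assumed stays. Since min(5, L) ≤ L, the first gap is at least 30 days. Since treatment ends no later than discharge (E ≤ L), the second is at least 25 days.

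**3. What the other routes cover**
- Section 8.1 covers measured hypotension. It also covers clinical hypotension, for which its examples are weakness, dizziness, faintness and chest discomfort. Headache, flushing and nausea are not among them.
- Section 8.1.1 covers whatever is found at the undefined scheduled evaluations, and whatever staff are told.
- Section 8.4.1 covers what reaches the records. It limits investigation to events that are not exempt, and does not define exempt.

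**4. What is left**

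Mild symptoms that nobody asks about in hospital and nobody charts reach the data only if the patient volunteers them, or recalls them at the call. Recall has two weaknesses. Read literally, a question about the time since the previous visit may not reach back to the six-hour treatment period. And the text on secondary endpoints in section 10.4.3 already doubts that patients can recall their baseline accurately for a scale used at six hours, whereas section 8.3 requires onset and end dates and duration for every event.

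**The case against.** Four points can fairly be made against this.

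**Harms are not left undetected.** A reader might infer from the blank cells that treatment harms go unobserved. The documents do not support that. Hypotension is measured and its symptoms prompt immediate assessment, staff have a duty to record at scheduled evaluations as well as on report, and records are reviewed. This point stands, and it narrows the gap to mild, uncharted symptoms.

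**Late reports are not excluded.** A reader might also infer that an event first mentioned at the call falls outside the reporting period and would be discarded. Section 8.1.1 tests when an event emerges, not when it is reported, so a day-1 headache described at day 30 still counts. The gaps above therefore measure recall delay, not exclusion. Nor do the documents say how often such symptoms reach a discharge summary, so no claim is made about that.

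**The schedule may not be exhaustive.** The adverse-event row is also blank at screening, where section 7.3.1 lists an inquiry. The data-collection row is marked only at T00 and 30 days, although data are collected in between. The footnote to the clinical-assessment row and the treatment algorithm are not in the text I could read, and either might mention symptoms. This is a real limit. But if sites already ask in hospital, the protocol should say so, and the fix merely records it.

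**This is a 70-patient pilot of approved drugs.** The named safety parameters (mortality, re-hospitalisation, ED visits, hypotension) do not depend on the open question. That limits the weight of the point but does not remove it, because section 10.4.5 also reports other safety events.

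**Conclusion.** The point holds in limited form. After treatment starts, the visible plan schedules adverse-event assessment only at the 30-day follow-up, at least 25 days (section 8.4.1 period) or 30 days (section 8.1.1 period) after reporting closes, and about 67 to 77 days after if the full call allowance is used with stays of 1 to 10 days. The consequence is confined to mild, transient, patient-reported effects such as headache, flushing and nausea. It does not extend to hypotension or to events that are charted.

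This rests on two assumptions: that the follow-up visit in section 8.1.1 is the 30-day call, and that the unseen footnote and algorithm schedule no adverse-event question. The disagreement between the two reporting periods is a separate matter; the gap exists under either. The change is worth making, but the primary endpoint and the named safety parameters do not depend on it.

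**What to change.** - In section 7.3.4, mark adverse-event assessment at T02-04, T06 and Day 2-6 (or discharge), where clinical assessment and vital signs already take place.
- In section 8.1.1, state that these contacts are the scheduled safety evaluations. Word the question so that it covers the time since treatment began.
- Ask the same open, non-leading question in both arms. If a checklist is added, it should cover the section 2.3.1 risks of both nitrates and diuretics. A list weighted to nitrate symptoms and read out by unblinded staff could itself create a difference between arms.
- Keep the 30-day call for vital status, re-hospitalisation and ED visits, and flag adverse events first reported there as retrospective.
- Align sections 7.3.3, 7.3.4, 8.1.1 and 8.4.1, including the two reporting periods, which must be reconciled.

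The cost is a change to the schedule and wording, a short question at contacts that already occur, and more minor events to record and review. Treatment, sample size and the analysis methods are unchanged.

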6.1.2 DURATION OF THERAPY

Both arms will continue until 6 hours after randomization. 6 hours was chosen to avoid confounding by patients with overly long ED LOS. At minimum, patients should receive at least one round of treatment. The protocol continues even if patients reach the floor. However, if in the opinion of the investigator, the protocol should not be continued once on the hospital floor, this is allowed and should be marked on the case report.

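### The adverse-event reporting window is defined inconsistently, and one definition closes it at discharge, so capture of later non-fatal events would depend on length of stay

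*Combined protocol and SAP*

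**What the plan says.** The combined protocol and SAP describes the collection of adverse events (AEs) in several places.

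- **End of the window, 8.1.1:** "The AE and SAE reporting period extends to day 5 of hospitalization or discharge, whichever comes first, unless otherwise specified".
- **Start and end of the window, 8.4.1:** AE reporting "begins after informed consent is obtained and initiation of study treatment and for 5 days after ending study treatment". Discharge does not close it.
- **Length of treatment, 6.1.2:** "Both arms will continue until 6 hours after randomization".
- **Schedule of events, 7.3.4:** the row "Assessment of AE/SAE's" has one mark, under the 30-day follow-up. The Day 1 and Day 2-6 columns are empty in that row.
- **Questioning the patient, 8.1.1:** "During the follow up visit, the Investigator will question the patient about adverse events using an open question".
- **Content of the 30-day call, 7.3.3:** the call is made "to assess vital status and re-hospitalizations or ED visits". AEs are not on that list, and there are no in-person visits after discharge.
- **Chart review, 8.4.1:** "Subject's hospital discharge summaries will be examined at hospital discharge and all non-exempt AEs will be investigated".
- **Start of collection:** 7.3.1 lists "Inquiry about Adverse events" among the screening procedures, and 5.3 has serious AEs reported from signature of consent for screen failures. Section 8.4.1 starts only once treatment has begun.

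Section 10.4.5 compares safety events between arms by frequency and percentage, with a chi-square or Fisher test and no allowance for time observed. Section 10.6.1 states that the trial is unblinded.

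**The concern.** Objective 1 asks whether the nitrate-intense strategy reduces congestion safely, so the count of AEs per arm is part of the answer. A window that closes at discharge gives each patient a different observation time, and that time can itself be affected by treatment. The strategies differ in how fast they may relieve congestion, and the clinicians who decide on discharge know the arm. Were one arm to go home sooner, it would have less time in which an AE could be recorded.

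The window also helps to decide what counts as an AE. Most of the categories listed in 8.1.1 are tied to the reporting period. An event must be an AE before 8.1.2 can class it as serious, and the expedited reports in 8.4.2 follow from that. Two sites reading different sections could therefore handle the same event differently.

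**Working it through.** The plan states no figure on this point to reproduce. The check compares the two windows directly and then asks what the gap could do to a comparison of the arms.

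**1. Length of each window**

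- Window A (8.1.1) = min(length of stay, 5 days). Stay is counted here from the start of treatment, as a simplification.
- Window B (8.4.1) = treatment time + 5 days. Treatment is at most 6 h = 0.25 day (6.1.2), so B is at most 0.25 + 5 = 5.25 days.

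| Length of stay | A (days) | A / 5.25 |
|---|---|---|
| 6 hours | 0.25 | 5% |
| 1 day | 1 | 19% |
| 2 days | 2 | 38% |
| 3 days | 3 | 57% |
| 4 days | 4 | 76% |
| 5 days or more | 5 | 95% |

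If treatment ended almost at once, B would be 5 days, and the shares for 1 and 2 days would be 20% and 40%. The two rules nearly agree only for stays of 5 days or more. Short stays are foreseen: 6.1.1 allows for discharge from the ED, and a note to 7.3.4 allows for discharge from an observation unit.

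**2. Share of time is not share of events**

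The documents give no AE rate over time. With a constant hazard, the shares of expected events equal the shares of time above. If the hazard instead halves each day (also an assumption, but plausible after a 6-hour treatment), the share for a stay of L days is (1 − 0.5^L) / (1 − 0.5^5.25):

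- 1 day: 0.500 / 0.974 = 51%
- 2 days: 0.750 / 0.974 = 77%

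**3. Possible effect on the comparison of arms**

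The documents give no length of stay by arm. Assume the same true risk in both arms, 30% over 5.25 days. The cumulative hazard is −ln(0.70) = 0.357, and the recorded risk is 1 − exp(−0.357 × share).

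| Assumed stays, arm 1 vs arm 2 | Constant hazard | Hazard halving daily |
|---|---|---|
| 3 vs 3 days | 18.4% vs 18.4% | 27.4% vs 27.4% |
| 3 vs 4 days | 18.4% vs 23.8% | 27.4% vs 29.1% |
| 2 vs 4 days | 12.7% vs 23.8% | 24.0% vs 29.1% |

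The spurious difference is zero with equal stays. In the unequal rows it runs from under 2 to about 11 percentage points, depending wholly on the assumptions. With one fixed window it is zero for any pattern of stays, apart from death and loss to follow-up.

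**4. The 30-day contact**

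The schedule places AE assessment at 30 days, and 8.1.1 has an open AE question at a follow-up visit. The only contact after discharge is the phone call, and 7.3.3 leaves AEs out of it. The call also comes after both windows have closed, and no rule says which of the events then reported are to be recorded.

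**5. A case that falls between the rules**

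Take a patient discharged on day 1 and readmitted on day 3 with a new problem. This is inside window B and outside window A. The readmission is counted as a 30-day outcome either way. Whether it is also a serious AE subject to 8.4.2 depends on which section is followed.

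**The case against.** The best reply starts from the closing words of the 8.1.1 sentence, which yield to anything specified elsewhere. Section 8.4.1 is the reporting procedure and does specify something else, so the 5-day rule may be the operative one. That reading is reasonable and may be what the sponsor intended. But no section says so, and 8.1.1 would still need correcting.

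The second reply is that little is lost. Much of this stands. Mortality, re-hospitalization and ED visits are followed to 30 days as safety outcomes (8.1, 8.4.1). Hypotension during a 6-hour treatment falls largely inside either window. Four stronger readings are tempting, and the documents do not support them:

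- **The safety comparison is biased towards one arm.** No length of stay or AE rate is given for either arm, and 7.1.2 returns both arms to standard care after the ED phase. A difference in discharge timing is possible, not shown.
- **Kidney injury after discharge is missed because of the window.** Section 7.2.1 says that no labs are drawn for the study, and 8.1.1 counts a laboratory abnormality only if it leads to new treatment. An unmeasured change would be missed under either rule.
- **Any event after early discharge is lost.** One that leads to an ED visit or admission enters the 30-day outcomes.
- **AEs are not collected in hospital because those schedule cells are empty.** Section 8.1.1 has staff record events whenever they learn of them, and 8.4.1 requires review of discharge summaries. The gap is in the schedule.

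It is also fair to say that this is a 70-patient pilot of approved drugs, and that the AE window feeds neither the primary endpoint nor the sample size.

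**Conclusion.** The inconsistency is on the page and should be reconciled. Sections 8.1.1 and 8.4.1 give different ends to the AE window. For stays of 1 and 2 days the first covers about 19% and 38% of the second, given treatment of at most 6 hours. Sections 7.3.3, 7.3.4 and 8.1.1 disagree on whether AEs are sought at the 30-day contact.

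If the discharge rule is followed, AE capture depends on length of stay, and the crude percentages in 10.4.5 would favour an arm discharged earlier. The direction follows from the rule. Whether it would happen, and how large it would be, cannot be known from the documents.

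What is exposed is narrow: non-fatal AEs after early discharge that cause no ED visit or readmission, and the status of post-discharge events within 5 days as reportable serious AEs.

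**What to change.** Reconcile 8.1.1, 8.4.1, 7.3.3 and 7.3.4 as follows.

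1. State one start, and one fixed end that is the same for every randomised patient whatever the discharge date. The window already in 8.4.1 would serve. Remove the discharge cut from 8.1.1, or have 8.1.1 refer to 8.4.1. Align the AE inquiry at screening with the chosen start.
2. Add the open AE question to the 30-day call in 7.3.3. Say that events with onset inside the window are recorded as AEs, and how later ones are handled.
3. Mark the in-hospital columns of the AE row in 7.3.4.

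The cost is protocol wording and one more question in a call that already takes place, with no added visits, tests or patients. The drawback is some recall error for events after discharge, since the call comes at 30 days or later. Chart review can offset part of this. The change will not recover laboratory changes that nobody measured.
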